## 9.3 Interim analyses and Stopping Rules – N/A

No interim analysis is planned for this study. AEs and SAEs will be monitored throughout the study, but no safety or efficacy issues are anticipated as the intervention has been well studied and efficacy has been established. The novel approach of this pilot is the integration of the intervention into the primary care setting.

## 9.4 Outcomes

While this pilot study is not powered to detect statistically significant changes in outcomes, we will analyze the outcomes as a feasibility test.

### 9.4.1 Primary outcome

The primary outcome is hospital transfers (hospitalizations, emergency department visits, observation stays without admission), and will be collected on each enrolled patient over a 7-month period. Per the table above, data will be collected monthly for the 3 months prior to enrollment, the 3 months during enrollment, and one month post enrollment.

### 9.4.2 Secondary outcomes

The secondary outcomes are number of total medications, number of anti-psychotics, acetylcholinesterase inhibitors, and memantine medications and will be collected on each enrolled patient over a 7-month period. Per the table above, data will be collected monthly for the 3 months prior to enrollment, the 3 months during enrollment, and one month post enrollment.

## 9.5 Data Analyses

A total of 150 PLWD and their care partners receiving care at one of three primary care practices at two health care organizations will be enrolled in the intervention to maximize the likelihood that this pilot study will support the feasibility, generalizability, and scalability to a full-scale ePCT. Data on an additional 100 patients will be extracted for data validation. Data collected during the pilot study will help inform the full ePCT by testing implementation and data collection procedures. Because patients will be enrolled on a rolling basis, we will establish the measurement periods individually for each patient, e.g., for the primary outcome of hospital transfers, we will measure the number of monthly hospitalizations over a 7-month period: three months prior to enrollment, three months during, and one month post discharge from the program. This will allow us to compare the baseline rate (rate of hospitalizations per 1,000 person-days prior to enrollment) with the hospitalization rate in the three months while the patient is enrolled. We will also collect data from the month following program discharge to assess whether hospitalization rates are maintained. We will follow a similar strategy for the secondary outcome of total number of active medications per month. Only exploratory analysis will be performed on the pilot data due to lack of a comparison/control population and low sample size. Descriptive statistics of the study population characteristics and outcomes will be calculated, including stratification at both the cluster and demographic level to identify potential disparities. Outcomes will be compared between the pre- and post-intervention time periods to estimate the effect size of the intervention and will be evaluated using repeated measures ANOVA, though the sample size of the pilot study may not permit definitive results. The R programming language will be used to carry out analysis. Survey results will be reported using descriptive statistics (means and standard deviations for continuous variables and frequency percent for discrete variables) to summarize individual survey items along with histograms for distributions of variables and bar charts/other charts to present the data. To plan for the full trial, we will conduct exploratory analysis to determine measurement reliability and the rate of missingness of patient level (baseline outcome rates, age, sex, race/ethnicity, and comorbidities) and cluster level covariates.

Data on fidelity of the intervention as well as process measures to assess feasibility are described in [Section 5.4 Adherence Assessment](#) and will be reported in the overall presentation of results.

Program satisfaction surveys will be analyzed descriptively and reported in aggregate.

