### **Sample Size and Population**

Using a pragmatic trial design, 150 community-residing PC PLWD will be enrolled in the program, each for a 3-month period. Data on an additional 100 PLWD will be pulled for validation purposes.

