### **3 STUDY DESIGN**

#### **3.1 Overview of study design and procedures**

Using a pragmatic trial design, 150 community-residing PC PLWD will be enrolled and receive MIND coordination services for 3 months to test program recruitment and implementation feasibility in PC practice settings. (An additional 100 patients will serve as a data validation arm to demonstrate the feasibility of collecting and validating data from large health systems and will not be enrolled in the intervention.) Enrollees will be recruited through EHR diagnosis and PC referrals. They will undergo a program intake screen (in-clinic or by phone) with a member of the PC team or the memory care coordinator (MCC) to establish program interest and identify the care partner. Interested and eligible enrollees will receive an office- plus home- or telephone/video-based dementia care assessment by the MCC with input from the PC care team. Assessment will be followed by collaborative family-centered care planning, and care plan implementation by an interdisciplinary PC-based team, supported by regular cased-based learning sessions. The primary (hospital transfers, i.e., admissions, ED visits, observation stays) and secondary outcomes (polypharmacy, antipsychotics, acetylcholinesterase, and memantine) will be obtained from regularly collected EHR data.

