## 9.2 Sample Size and Randomization

The pilot study is not powered to detect significant changes in our selected outcome measures. However, we estimated power, nonetheless. Preliminary studies of the MIND at Home program report a reduction from 1 to 0.73 in number of hospital admissions per year, or a 27% decrease. Our primary outcome is hospital transfers (which includes admissions but also ER visits and observation stays without admissions), but we expect that the relative effect size on this outcome will be similar to hospital admissions alone. Because our observation periods are 3 months (as opposed to 1 year), our assumed base rate is 0.50. To make our power estimates slightly conservative, we will assume an effect size of 25%. Given these factors, the estimated power is 37.5% to detect the effect (Z-test with square root adjustment for low base rates). This low power is primarily caused by the short duration of the intervention per patient in the pilot, making outcome observations (transfers) very rare. In the full trial we will use a 12-month intervention period.

For the full trial, sample size estimates will be based on the primary outcome (hospital transfer rate over 12 months). We intend to implement a cluster-controlled cohort design with a baseline period, which requires specialized power calculations (Hemming et al., 2020). Calculations will assume a Poisson distribution of hospitalization rates, equal cluster sizes, and an equal number of clusters in the treatment and control arms. Because validated estimates of correlations are not available, we will use conservative assumptions for intra-cluster correlation (0.05) and individual autocorrelation (0.2). Baseline hospital transfers are estimated to occur at a rate of 1 transfer per year. Assuming this rate, the study will be powered to detect a 0.2 absolute reduction (20% relative reduction) at greater than an 80% power level. This will require at least 11 clusters in each arm of two study arms, with each practice recruiting approximately 50 patients. Analysis of the full study will make use of mixed-model ANCOVA, controlling for both patient level and cluster level confounding variables.

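### Section 9.5 treats an uncontrolled pre/post change as the intervention's effect size, but with no comparison group it can only describe change, and regression to the mean could account for part or all of the assumed 25% fall

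*Combined protocol and SAP*

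**What the plan says.** Section 9.5 measures each enrolled patient for three months before enrollment, three months on the program and one month after discharge. It states the purpose of the comparison as "Outcomes will be compared between the pre- and post-intervention time periods to estimate the effect size of the intervention", by repeated measures ANOVA. It also gives a caveat: "Only exploratory analysis will be performed on the pilot data due to lack of a comparison/control population and low sample size". Section 9.1 says there is no statistical hypothesis, and section 9.4 presents the outcome analysis as a test of feasibility. Regression to the mean and time trend are not mentioned anywhere.

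On entry, section 3.1 says "Enrollees will be recruited through EHR diagnosis and PC referrals". Sections 4, 4.3 and 6.2.1 describe invitation at an office visit, and telephone contact for patients found in the EHR without a scheduled visit. Section 4 also allows referral from other providers.

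For size, the Précis says "150 community-residing PC PLWD will be enrolled in the program, each for a 3-month period". In section 9.2, "our assumed base rate is 0.50" (per 3 months), "we will assume an effect size of 25" percent, and "the estimated power is 37.5% to detect the effect". For the full trial the same section uses 1 transfer per year, which is 0.25 per 3 months.

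Of the non-enrolled cohort the Précis says "Data on an additional 100 PLWD will be pulled for validation purposes".

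**The concern.** With one group and no comparator, the pre/post contrast combines any program effect with whatever else changes around the time of enrollment. Two such influences are obvious here. The first is regression to the mean: the baseline window ends at enrollment, so if a recent hospital transfer makes an office visit, a referral or acceptance of the program more likely, the baseline is selected to be high. The second is time trend, including disease progression, which could push the rate up instead.

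The words exploratory and not definitive warn about precision and testing. They do not alter what section 9.5 says is being estimated. A report that follows the section as written could present a fall as the program's effect when the design cannot separate the two. The 25% assumption gives no independent reassurance: it is rounded down from a 27% reduction in admissions that section 2.2 describes as a pre-post analysis of program recipients, also without a control.

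**Working it through.** **1. The plan's own figure.** Inputs from section 9.2 and the Précis: 150 patients, 0.50 before and 0.50 × 0.75 = 0.375 during, square-root Z-test. Alpha and sidedness are not stated; 0.05 two-sided is assumed, with the periods treated as independent.

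- Difference: √0.50 − √0.375 = 0.0947.
- SE: 0.5 × √(2/150) = 0.0577.
- Power: Φ(0.0947/0.0577 − 1.96) = 37.5%, as stated.

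The assumed effect is therefore 75 transfers before (150 × 0.50) against 56.25 during (150 × 0.375), a difference of about 19.

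**2. Spurious fall with no program effect, same rate in every patient.** Let m be the true 3-month rate and f the share of enrollees who enter because they had at least one transfer in the prior 3 months. The values of f are assumptions. Then

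baseline = (1 − f)m + f × m/(1 − e^(−m)); on-program rate = m; fall = 1 − m/baseline.

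For m = 0.25 and f = 0.10: baseline = 0.225 + 0.10 × 1.130 = 0.338, so the fall is 1 − 0.25/0.338 = 26%.

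**3. The same, with rates varying between patients.** Take gamma-distributed rates with shape k = 0.5, also an assumption. Among patients with a prior transfer:

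- P = 1 − (k/(k+m))^k;
- prior mean = m/P;
- later mean = [m − m(k/(k+m))^(k+1)]/P.

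For m = 0.50: P = 0.293, prior mean 1.707, later mean 1.104. With f = 0.10 the rate goes from 0.45 + 0.171 = 0.621 to 0.45 + 0.110 = 0.560, a fall of about 10%.

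| Share f | m = 0.25, same rate | m = 0.25, k = 0.5 | m = 0.50, same rate | m = 0.50, k = 0.5 |
|---|---|---|---|---|
| 0% | 0% | 0% | 0% | 0% |
| 5% | 15% | 12% | 7% | 5% |
| 10% | 26% | 21% | 13% | 10% |
| 20% | 41% | 31% | 24% | 16% |

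**4. Share needed to mimic the full 25%.**

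- True rate 0.25: 9% (no heterogeneity) to 13% (k = 0.5).
- True rate 0.50: 22% to 42%.
- If the observed baseline is 0.50 and the observed on-program rate 0.375: 15% to 18%, or about 23 to 26 of 150 patients. With no heterogeneity, f = (0.50 − 0.375)/(1.199 − 0.375) = 0.152, where 1.199 = 0.375/(1 − e^(−0.375)).

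**5. Which sensitivity analysis works.** Dropping patients who had a transfer in month -1 forces that month to zero for those who remain. At a constant rate they have two months of events before against three after, a ratio of 3/2, or a spurious rise of 50%. Leaving month -1 out of the baseline for everyone, with a two-month denominator, avoids this. At the plan's rates it gives 50 expected baseline events, and the SE of the log rate ratio goes from √(1/75 + 1/56.25) = 0.176 to √(1/50 + 1/56.25) = 0.194. The 95% CI around 0.75 goes from 0.53–1.06 to 0.51–1.10 (Poisson).

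**6. The 100 as a comparator.** If they had the same 3+3 months of data at 0.25 to 0.50 per 3 months, the SE of the log ratio of rate ratios would be √(0.176² + 2/25) = 0.333 to √(0.176² + 2/50) = 0.267. Power for a 25% fall would be 14% to 19%.

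**The case against.** The plan is open about its limits: no control, exploratory analysis only, no hypothesis. That stands, and nothing is concealed. What is left is the stated use of the estimate, which those caveats do not change.

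The stronger objection is that selection on recent transfers is not shown. Eligibility in section 4.1 rests on a dementia code, a problem-list diagnosis or a medication. Patients in crisis are excluded (section 4.2), and telephone outreach reaches people with no scheduled visit. This also stands. A reader might infer that the rate is bound to fall without any program effect; the documents do not support that.

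A reader might also infer that a spurious fall would pass into full-trial sizing. Section 9.2 already sets those inputs (1 transfer per year, a 20% reduction) without using the pilot's change, so this is something to rule out in writing, not a stated plan.

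Finally, a reader might see the 100 validation patients as an unused concurrent control. Section 11.2.1.2 describes them as people who sought care in the past and are not seeking it now, and no index date or outcome window is stated for them. They would not share any visit- or referral-triggered entry. Their flat line beside a falling enrollee line could make an artefact look like an effect.

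**Conclusion.** The purpose stated in section 9.5 is wrong as written: the analysis can describe a change but cannot estimate the intervention's effect. The possible size is material. Shares of 5% to 20% entering because of a transfer give a spurious fall of about 7% to 24% at 0.50 per 3 months and 15% to 41% at 0.25, with no heterogeneity; strong heterogeneity (k = 0.5) brings these to 5% to 16% and 12% to 31%. Without such selection, regression to the mean contributes nothing. These figures show what is possible. They are not a forecast, because the documents give neither the share nor the spread of patient rates. The correction to the wording does not depend on them.

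**What to change.** In section 9.5:

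1. Replace the effect-size clause with *to describe the pre/post change, with 95% CI*. Add that this change is not an estimate of the program's effect, because regression to the mean and time trend cannot be excluded, and that it will not be used as the full-trial effect size.
2. Using the monthly counts already scheduled in the section 6.1 table, show transfer rates for months -3, -2 and -1 separately. Repeat the comparison with month -1 left out of the baseline for all patients. Do not drop the patients who had a transfer in that month.
3. Do not present the 100 validation patients as a concurrent control.

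The cost is one extra table and a more modest conclusion; no new data are needed. The table will be coarse: at 0.50 per 3 months each baseline month has about 150 × 0.50/3 = 25 transfers, and half that at 0.25. Leaving out month -1 does not remove selection on transfers in months -2 or -3, so a flat pattern lessens the worry without settling it.

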## 10 DATA COLLECTION AND QUALITY ASSURANCE

### 10.1 Data Collection Forms

Data will be collected from the EHRs of participating HCOs using existing data regularly collected to provide standard patient care and monitor quality, and through post program satisfaction survey data.

**Enrollment Feasibility (Aim 1).** Algorithms based on CMS' Chronic Care Warehouse definition of AD/ADRD will be deployed in each respective clinic EHR to identify eligible PLWD and standardize referral and enrollment protocols. To assess feasibility and validity of **eligible patient identification, referral, and enrollment**, MCCs will electronically record the number of patients flagged as eligible, referred, enrolled, and retained or who refused, were unreachable, or lost to follow-up. Referral, recruitment, patient acceptance, and attrition rates will be calculated to assess the feasibility of use of the algorithm and of the recruitment protocol (**Aim 1**). Attention will be paid to potential differential referral, enrollment implementation for PLWD of minority race/ethnicity and other underserved populations, e.g., rural residents. All data collected on participants will be collected electronically, using password-protected files and saved on password-protected computers.

**Program implementation feasibility (Aim 2).** Implementation feasibility will be assessed by collecting a standard set of process measures and fidelity metrics. For all participant dyads, process measures will be collected by the MCC and submitted monthly to the AMGA research analyst including number, duration, type, and general content of encounters per dyad will be calculated to assess the feasibility of implementation. All process measures will be monitored and stratified by minority participants (rurality, race/ethnicity) to assess differential rates of adherence, attrition/retention. Fidelity will be assessed by tracking completion of core intervention components (# needs assessment completed, # care plans completed, # completed 3 months, # with MCC encounter at least every 3 months), and attendance at weekly virtual learning sessions by team member types (>50% of sessions). Collection of this information is facilitated by documents created for MIND on program implementation fidelity. (See [Appendix A](#).) Fidelity measures will be captured and monitored using a work process template/spreadsheet completed by MCCs for each assigned dyad for each encounter. The template serves as an operations checklist the MCC completes at each home visit/contact that includes each component of the home, telephone, or video visit, the care plan with needs being addressed, actions taken, and follow up plans. All data collected on participants will be collected electronically, encrypted during upload, download, and transfer, using password-protected files, and saved on password-protected computers.

A de-identified version of the management template will be shared with the co-investigators (Drs. [name] & [name]) biweekly (i.e., every other week) for review and feedback. De-identified program implementation data will be sent by the study site to the AMGA research analyst monthly. Acceptability will be assessed from multiple stakeholder perspectives. In the final 2 months of the pilot, brief surveys developed in prior MIND studies will be sent (email or mail) to dyads (post program) to assess experience (satisfaction, perceived benefit, challenges, ways to improve program). The participant survey is included in the Appendix.

**Patient-level outcomes (Aim 3).** All outcomes' data will be collected from the participating HCOs' respective EHRs using existing data regularly collected to provide standard patient care and to monitor quality. Participants enrolled in the intervention will be 'flagged' in the EHR as pilot participants and monitored longitudinally.

Monthly data will be submitted to AMGA at the end of study months three, seven, and 10 (see milestones and timeline). (A test dataset will be sent after month one for review and feedback.) Seven total months of EHR data will be collected from each participant: three months prior to enrollment, three months during the intervention, and one month post program discharge. The **primary outcome** is rate of hospital transfers (per 1,000 person-days), including hospital admissions, emergency department visits, and observation stays (non-admissions). The **secondary outcome** is total number of active medications for enrolled PLWD. Accuracy of ascertainment will be tested through chart review. All data collected on participants will be collected electronically, using password-protected files and saved on password-protected computers. Data will be transferred to AMGA using a secure Dropbox folder that is encrypted when data are uploaded and downloaded and during transfer.

## 10.2 Data Management

Clinic study sites are responsible for data collection and management as described above. MCCs will collect data on study feasibility, validity of patient identification, and intervention fidelity. Information technology staff at participating organizations will be responsible for extracting data on participants from their EHRs and working closely with the AMGA research analyst during the file transfer process to ensure confidentiality and protection of participant data.

AMGA staff will be responsible for working closely with clinic site investigators and clinic staff in the collection of study data. Once data are transferred through a secure Dropbox link, AMGA staff will be responsible for maintaining and protecting the confidentiality of all study data. AMGA staff will keep the

password-protected files on secure servers on password-protected computers. Only the AMGA research analyst, biostatistician, and study PI will have access to study data.

Study feasibility, validity, and fidelity data will be collected using Excel spreadsheets that are password protected. EHR data will be abstracted by the study sites using their usual methods of extracting data for quality purposes. Data will be sent to AMGA as csv files.

### **10.3 Quality Assurance**

#### **10.3.1 Training**

All study staff at each study site will take the online NIH Good Clinical Practice training. A link to the free NIH training has been provided to each study site. The study site investigators will report to the PI when all staff have been trained and will provide certificates of completion.

#### **10.3.2 Quality Control**

AMGA research staff will conduct quality control on all data collected for research purposes. This entails running frequencies for all variables, looking for invalid entries, and identifying values that exceed those that are physiologically possible. Values are also evaluated for reasonableness in relation to published or previously reviewed data. Data and analytic code are reviewed by a minimum of two AMGA research staff throughout data collection and analysis, and documentation is generated for any errors and corrective action. In the case of suspected data errors, AMGA staff will contact data providers directly to validate data quality.

#### **10.3.3 Metrics**

For outcome measures of hospitalizations and medications, quality control metrics will include mean, medians, maximum and minimum values, standard deviations, and inter-quartile range. These values can be compared across study sites, across data storage locations (e.g., primary data reporting forms and analytic databases), and across time to identify potentially erroneous data reports.

